##### **4.4.2. Handling of Subject Withdrawals or Termination**

If a subject is removed or withdraws from the study, the date and reason for withdrawal will be recorded on the appropriate electronic case report form (eCRF). If the subject is withdrawn due to an AE or SAE, the Investigator should follow the subject until the AE/SAE has adequately resolved, stabilized, or is explained.

If a subject is unable to complete follow-up or cannot be contacted by telephone, 3 separate telephone calls should be made to obtain subject related safety information. All attempts should be documented in the source documents. If the subject does not respond to the 3 telephone calls, then the investigator **MUST** send a certified letter to the subject. If the subject does not respond to the letter within 4 weeks, then the subject will be considered "lost to follow-up" for the study.

Subjects who have signed the ICF but are found to be ineligible **PRIOR** to insertion of the study catheter will be recorded as screen failures in the eCRF.

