### Endpoint:

#### Primary Endpoints:

- **Safety**

Incidence of early onset Primary Adverse Events (PAEs) (within 7 days of an ablation procedure which uses the HELIOSTAR™ catheter). PAEs include the following adverse events (AEs) and are defined in section 9.2.3 of the protocol:

- Device or procedure related death\*
- Atrio-Esophageal Fistula\*
- Myocardial Infarction
- Cardiac Tamponade/Perforation\*
- Thromboembolism
- Stroke/ Cerebrovascular Accident (CVA)
- Transient Ischemic Attack (TIA)
- Phrenic Nerve Paralysis (permanent)
- Pulmonary Vein Stenosis\*
- Pericarditis
- Pulmonary Edema
- Major Vascular Access Complication/Bleeding
- Hospitalization (initial or prolonged)\*\*

\* Events are considered and analyzed as primary AEs **even if they occur greater than one week (7 days) post-procedure.**

\*\* Excludes hospitalization solely due to arrhythmia recurrence or non-medically urgent cardioversion.

- **Effectiveness**

Freedom from documented asymptomatic and symptomatic Atrial Fibrillation, Atrial Tachycardia, or Atrial Flutter of unknown origin+ episodes based on electrocardiographic data (≥30 seconds on arrhythmia

monitoring device) through the effectiveness evaluation period (91-365 days post index procedure). Additionally, if a subject meets any one of the following criteria, then the subject will be considered an effectiveness failure:

- Failure to achieve acute procedural success. Acute procedural success is defined as confirmation of entrance block in clinically relevant PVs (all PVs except those that are silent and/or cannot be cannulated) after adenosine and/or isoproterenol challenge (with or without the use of a focal catheter).
- Greater than 2 repeat ablations for AF/AT/AFL (of unknown origin\*) in the blanking period ( $\leq 90$  days post index procedure) or a repeat ablation or surgical treatment for AF/AT/AFL (of unknown origin\*) during the effectiveness evaluation period.
- Direct current (DC) cardioversion for AF/AT/AFL (of unknown origin\*) during the effectiveness evaluation period.
- Continuous AF/AT/AFL (except CTI dependent) on a standard 12-lead ECG during the effectiveness evaluation period.
- A Class I and/or Class III AAD is prescribed/taken for atrial arrhythmia other than CTI dependent AFL at any time beyond the 3-month follow-up visit window (i.e., at any time beyond day 105 to 365 post index procedure).
- Oral Amiodarone is prescribed post index ablation procedure.

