## 5. Responsibilities

### 5.1. Investigator Responsibilities

Investigators at each participating clinical site will have the following responsibilities:

- Supervising the study at their respective site.
- Assuring compliance by site personnel within the provisions of the protocol.
- Providing the Sponsor with:
  - Signed, dated Investigator Agreement
  - Written institutional review board (IRB) / ethics committee (EC) approval letters and IRB/EC-approved consent forms
  - Signed, dated Financial Disclosure form for each participating investigator
  - Curriculum vitae for each investigator
  - Copy of current medical license for each study investigator, as applicable.
- Maintaining an accurate and current Delegation of Authority log which identifies individuals authorized to perform work for the study.
- Completing the appropriate training on the device and the study protocol prior to enrolling and treating subjects.
- Maintaining accurate and current logs for the study as requested by the study team, including but not limited to:
  - Subject pre-screening log
  - Delegation of authority log
  - Device Accountability log
  - Adverse event log.

- Obtain initial and amendment (if applicable) IRB/EC approval and, if applicable, routine review/approval for the study protocol and informed consent as instructed by the IRB/EC.
- Obtain Patient ICF prior to subject participation.
- Perform medical procedures as described in this protocol.
- Order tests required by the study protocol.
- Follow subjects until the end of the study.
- Accurately complete and sign eCRFs in a timely manner.
- Maintain relevant source documentation and allow Sponsor direct access to perform monitoring or auditing duties.
- Maintain records and provide reports according to prevailing regulatory requirements.
- Share relevant study-related information with delegated study staff.
- Inform the appropriate entities (e.g., Sponsor, CA, IRB/EC) in a timely manner regarding the occurrence of AEs and/or product malfunctions/deficiencies.
- Immediately notify the sponsor of any pending Regulatory Authority audits/inspection at the study site and allow access to study records for authorized regulatory entities.
- Make sufficient effort to maintain contact with treated subjects who fail to comply with the follow-up requirements.

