## **7. Study Medications**

### **7.1. Antiarrhythmic drugs**

During this study, current AF management guidelines and the institution's standard of care practices are to be followed as closely as possible for AAD therapy.

A Class I and/or Class III AAD can be administered for AF and terminated before the end of the 3-month follow-up visit window (i.e., day 104). If a Class I/III AAD is prescribed/administered after day 104 post procedure or oral amiodarone is prescribed/administered at any time post procedure, it MUST be accompanied by documentation of arrhythmia. If a Class I and/or Class III AAD is continued or started past Day 104, the subject will be considered a primary effectiveness failure. If oral Amiodarone is prescribed and/or taken at any time post index ablation procedure, the subject will be considered a primary effectiveness failure.

Table 7.1A illustrates the corresponding status of primary effectiveness endpoints based on AAD therapy administered in the blanking and post-blanking periods.

[figure not shown]

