**Table 8.8A: Summary of Subject Assessments**

Assessments	Pre- Procedure	Pre- Discharge Post procedure - Discharge	D7  D7- 14	M1 D23- 37	M3 D76- 104	M6  D150- 210	M12 D315- 405	UNS
Patient Informed Consent/ Demographics	● 							
Height and Weight	● 							
Physical exam	● 	●		●	●	● 	●	●
Medical/AF history	● 							
Cardiac Medication Regimen 	● 	●	●	●	●	●	●	●
Anti-coagulation Regimen 	● 	●		●	●	●	●	●
CHA 2 DS 2 -Vasc Score	● 							
NYHA functional Class Scale	● 							
Pregnancy Test	● 							
QoL (AFEQT™ questionnaire) 	● 				●	● 	●	
TTE	● 	● 						
LA thrombus detection (TEE/ICE)	● 							
ECG	● 	● 		● 	●	● 	●	● 
TTM 				●	●	●	●	●
24-hour Holter 							●	
Cardiac CT/MRA	● 				● 			● 15a
Adverse events 	●	●	●	●	●	●	●	●
AFL/AT/AF recurrence 				●	●	●	●	●
Repeat Ablation				●	●	●	●	●
Cerebral MRI (NAE subjects only)	● 	● 		● 	● 	● 	● 	● 
Neurological Exam (NAE subjects only)	● 	● 		● 	● 	● 	● 	● 
NIH Stroke Scale (NAE subjects only)	● 	● 		● 	● 	● 	● 	● 
mRSE (NAE subjects only)	● 			●	● 	● 	● 	● 
MMSE (NAE subjects only)	● 			●	● 	● 	● 	● 

1. May be telephone call, virtual visit, or clinic visit.
2. Completed/Collected within 90 days prior to ablation procedure.
3. Required only for clinical visit
4. May be completed via telephone call or virtual visit when a clinic visit is not possible.
5. Completed/Collected in subjects with congestive heart failure.
6. In all women of childbearing age and potential. To be completed within 72-hours prior to ablation procedure.
7. To be completed within 48 hours post-index procedure.
8. To be completed the day before or the day of the study ablation procedure.

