### 9.2. Adverse Event Definitions

#### 9.2.1. Adverse Events (AE)

An AE is any untoward medical occurrence in a subject whether or not related to the investigational medical device. Specifically, an adverse event (AE) is any undesirable experience (sign, symptom, illness, abnormal laboratory value, or other medical event) occurring to a subject during the course of the study, whether or not it is related to the device or procedure.

The following clinical events **will not be considered an adverse event for this clinical study:**

- Any medical condition that is present at the time of screening. Such conditions should be added to the medical history, if not previously reported. However, if the study subject's condition deteriorates at any time during the study, it should be recorded as an AE.
- A trace / trivial / minor pericardial effusion that is asymptomatic, requires no medical intervention, and does not extend hospitalization will not be considered an adverse event
- Minor pericarditis attributable to the ablation procedure defined as pleuritic chest discomfort with or without pericardial rub and ECG changes.
- Recurrence of pre-existing AF/AT/AFL
- AF/AFL/AT recurrence requiring DC cardioversion during the blanking period and/or pharmacological cardioversion at any time throughout the duration of the study. However, new onset of left atrial flutter occurring post-ablation is an AE.
- Re-ablation for AF or pre-existing AFL/AT itself is not an AE, however any complication associated with the repeat ablation procedures is considered an AE and shall be reported within the applicable timelines.

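### The last-contact calls in Protocol 4.4.2 seek only safety information, so primary effectiveness failures, above all repeat ablation, may go unasked in reachable subjects who have stopped follow-up

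*Protocol*

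**What the plan says.** Protocol 4.4.2 covers subjects who cannot complete follow-up as well as those who cannot be reached. It states one purpose for the contact attempts: "3 separate telephone calls should be made to obtain subject related safety information". A certified letter follows, with no content specified. "If the subject does not respond to the letter within 4 weeks, then the subject will be considered" lost to follow-up. Section 5.1 adds a general duty, "Make sufficient effort to maintain contact with treated subjects who fail to comply with the follow-up requirements", and is also silent on what to ask.

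The primary effectiveness definition in the Protocol Summary counts as failures, among others, "a repeat ablation or surgical treatment for AF/AT/AFL" and "Direct current (DC) cardioversion for AF/AT/AFL" in the evaluation period, and oral amiodarone at any time after the index procedure. Section 7.1 adds: "If a Class I and/or Class III AAD is continued or started past Day 104, the subject will be considered a primary effectiveness failure".

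On adverse events, section 9.2.1 says "Re-ablation for AF or pre-existing AFL/AT itself is not an AE" and also excludes recurrence of pre-existing AF/AT/AFL. In Table 8.8A, footnote 4 reads "May be completed via telephone call or virtual visit when a clinic visit is not possible". It is attached to the cardiac medication, arrhythmia recurrence and adverse event rows, among others. It is not attached to the Repeat Ablation row.

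**The concern.** The calls in 4.4.2 may be the last chance to learn what happened to a subject who has left the schedule. Their stated content does not match the primary effectiveness endpoint. Several failure components are events a patient can report by telephone and a provider's records can confirm, but most of them are not adverse events under this protocol, so a safety question need not bring them out.

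This matters more than usual here. The SAP (section 1) describes a single-arm study against performance goals, so no control arm shares the error. A subject whose arrhythmia returned and who sought a further procedure or drug elsewhere is a plausible non-attender, so missingness may be related to outcome. Such a subject also misses the 12-month ECG and the only 24-hour Holter (section 8.6). Reported procedures, drugs and outside tracings may then be the main remaining evidence.

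**Working it through.** The plan states no figure on this point, so the main check sets the sections side by side.

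| Primary failure component | Adverse event under 9.2.1? | Telephone route in Table 8.8A | Named in 4.4.2? |
|---|---|---|---|
| Repeat ablation or surgery | Repeat ablation for AF or pre-existing AFL/AT: no, though its complications are. Surgery: not addressed | Row present, no footnote 4 | No |
| Class I/III drug past day 104; oral amiodarone | Starting a drug is a treatment, not an event in itself | Cardiac medication row, footnote 4 | No |
| Arrhythmia documented elsewhere | Recurrence of pre-existing AF/AT/AFL: no. New-onset left atrial flutter: yes | Recurrence row, footnote 4 | No |
| DC cardioversion in the evaluation period | Not excluded; the exclusion covers DC cardioversion in the blanking period only | No row of its own; the adverse event row has footnote 4 | May surface as safety information |

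**Who is affected.**
1. Subjects never reached give no data, whatever the script says.
2. Subjects who withdrew consent to further contact should not be questioned.
3. Subjects still on schedule who miss a clinic visit can give medication and recurrence by telephone under footnote 4. The 6-month visit may itself be a call (footnote 1).
4. Subjects who have stopped scheduled visits but answer a 4.4.2 call are the gap, for the time since their last completed contact. Failures recorded earlier, including on core-lab-read transtelephonic tracings, remain known.

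**Scale, on assumptions only.** N = 400 is the SAP maximum. The documents give none of the following, so they are assumed:
- L, the share off follow-up: 5% or 10%, that is 400 × 0.05 = 20 or 400 × 0.10 = 40 subjects.
- q, the share of those who truly failed after last contact in a reportable way: 20% to 60%. The rest are taken as true successes.
- s, the success rate in completers: 60% or 70%.

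The error in the estimated success rate depends on how unknown subjects are handled:
- Counted as successes: error = +L × q. At 5%: 0.05 × 0.20 = +1.0 to 0.05 × 0.60 = +3.0 points. At 10%: +2.0 to +6.0 points.
- Excluded: the truth is (1 − L)s + L(1 − q), so error = L × (s − (1 − q)). At 5%: 0.05 × (0.60 − 0.80) = −1.0 to 0.05 × (0.70 − 0.40) = +1.5 points. At 10%: −2.0 to +3.0 points.
- Counted as failures: error = −L × (1 − q). At 5%: −0.05 × 0.80 = −4.0 to −0.05 × 0.40 = −2.0 points. At 10%: −8.0 to −4.0 points.

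These figures cover all subjects off follow-up, as if none had already failed on record. The calls can change results only for the share actually reached. The figures are therefore outer limits under the stated assumptions and do not estimate the benefit of the fix.

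**The case against.** A reader might infer that every such failure is lost: redo procedure, cardioversion, drug or outside recurrence. The documents do not support that. Footnote 4 gives medication and recurrence an explicit telephone route when a clinic visit is not possible. Section 8.6 requires drug type, indication and dates, and makes the recurrence item cover arrhythmia found on other devices. DC cardioversion is left out of the adverse event definition only in the blanking period, whereas the failure criterion concerns the evaluation period, so a safety question could elicit it. Section 5.1 also requires subjects to be followed to the end of the study, section 17.1.3 has the sponsor track missing data and instruct sites on reducing it, and nothing forbids asking about rhythm or procedures.

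These points stand, and they narrow the gap. They do not close it. Footnote 4 belongs to the visit table and 4.4.2 does not invoke it. It does not reach the Repeat Ablation row at all. The general duties in 5.1 and 17.1.3 set no content for the calls.

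**Conclusion.** The point holds as a modest gap between two parts of the protocol. The calls are limited to safety information, and the adverse event definition leaves out recurrence and repeat ablation. For reachable subjects off schedule, primary failures since the last completed contact may therefore go unasked. The gap is clearest for repeat ablation. It extends to Class I/III drugs, oral amiodarone and outside-documented arrhythmia, which can be collected by telephone only as scheduled-visit items.

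It is also tempting to conclude that the success rate will be overstated by a known amount. That does not follow. In the illustration the error runs from +6.0 to −8.0 points depending on the handling rule, and neither that rule nor an attrition rate is in the public text. Their absence there is not a fault of the plan. The case for change is that it obtains facts cheaply that a missing-data rule would otherwise have to assume.

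One limit applies. Asymptomatic episodes count, so a negative answer by telephone does not establish success. The calls can reveal failures but cannot replace the missed ECG and Holter.

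**What to change.** - In 4.4.2, state that the calls and the certified letter seek safety information and primary effectiveness status since last contact, unless the subject has withdrawn consent to further contact.
- List the items: repeat ablation or surgery for AF/AT/AFL; DC cardioversion; Class I/III drug or oral amiodarone, with dates and indication; any arrhythmia documented on any device.
- Request source records for each positive answer, enter it in the eCRF with its date, and apply the existing failure criteria unchanged.
- Record negative answers with their dates too. If positive answers came back as failures while negative answers stayed excluded, the estimate would lean low.
- Attach footnote 4 to the Repeat Ablation row of Table 8.8A.

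The cost is protocol wording, a short script, a few extra minutes on calls already required, and some outside-record requests, not all of which will succeed. Endpoint, treatment and sample size do not change.

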#### **4.5. Subject Accountability**

- **Pre-Screen Failure:** Patients that are pre-screened, but do NOT sign an ICF. Information on reasons for pre-screen failures will be captured and descriptive analysis will be performed.
- **Enrolled Subjects:** Subjects who sign the study ICF.
  - **Excluded Subjects:** Subjects who are enrolled but never undergo insertion of the study catheter. Excluded subjects will not be included in the primary endpoint analyses and will only be followed between the time of ICF signature and exclusion from the study for adverse event reporting. Subjects who signed the ICF but are found to be ineligible prior to the procedure will be recorded as screen failures in the eCRFs.
  - **Evaluable Subjects:** All enrolled subjects who have the study catheter inserted.

- **Roll-In Subjects:** Enrolled Subjects who have the study catheter inserted and RF delivered with the study catheter during the Roll-In phase of the ablating investigator. These subjects will not be included in the primary endpoint analyses and will be analyzed separately.
- **Discontinued Subjects:** Evaluable subjects who have the study catheter inserted but do not undergo ablation (i.e., no RF energy is delivered with the study catheter). Discontinued subjects will remain in follow-up for 3 months post catheter insertion. If a SAE is reported for a discontinued subject, the subject will be followed until event resolution (with or without sequelae), stabilization, or until the event is adequately explained.
- **Lost to Follow-up Subjects:** Subjects who are enrolled and evaluable, but contact is lost after most recent follow-up visit (despite 3 documented attempts to contact the subject).
- **Withdrawn / Early Termination Subjects:** Subjects who withdraw consent for study participation or are withdrawn/terminated from the study by the investigator prior to completion of all follow-up visits.
- **Completed Subjects:** Enrolled subjects who have not been excluded, discontinued, withdrawn, terminated early, or lost-to-follow-up prior to the final study visit.

## 5. Responsibilities

### 5.1. Investigator Responsibilities

Investigators at each participating clinical site will have the following responsibilities:

- Supervising the study at their respective site.
- Assuring compliance by site personnel within the provisions of the protocol.
- Providing the Sponsor with:
  - Signed, dated Investigator Agreement
  - Written institutional review board (IRB) / ethics committee (EC) approval letters and IRB/EC-approved consent forms
  - Signed, dated Financial Disclosure form for each participating investigator
  - Curriculum vitae for each investigator
  - Copy of current medical license for each study investigator, as applicable.
- Maintaining an accurate and current Delegation of Authority log which identifies individuals authorized to perform work for the study.
- Completing the appropriate training on the device and the study protocol prior to enrolling and treating subjects.
- Maintaining accurate and current logs for the study as requested by the study team, including but not limited to:
  - Subject pre-screening log
  - Delegation of authority log
  - Device Accountability log
  - Adverse event log.

- Obtain initial and amendment (if applicable) IRB/EC approval and, if applicable, routine review/approval for the study protocol and informed consent as instructed by the IRB/EC.
- Obtain Patient ICF prior to subject participation.
- Perform medical procedures as described in this protocol.
- Order tests required by the study protocol.
- Follow subjects until the end of the study.
- Accurately complete and sign eCRFs in a timely manner.
- Maintain relevant source documentation and allow Sponsor direct access to perform monitoring or auditing duties.
- Maintain records and provide reports according to prevailing regulatory requirements.
- Share relevant study-related information with delegated study staff.
- Inform the appropriate entities (e.g., Sponsor, CA, IRB/EC) in a timely manner regarding the occurrence of AEs and/or product malfunctions/deficiencies.
- Immediately notify the sponsor of any pending Regulatory Authority audits/inspection at the study site and allow access to study records for authorized regulatory entities.
- Make sufficient effort to maintain contact with treated subjects who fail to comply with the follow-up requirements.
- Maintaining study records for at least 2 years, or as specified per country specific record retention requirements, after the study is completed and or terminated. The Sponsor will notify the Investigator of either of these events.
- Comply with IRB/EC and Sponsor annual report requirements, including the final report.

## **5.2. Sponsor Responsibilities**

The Sponsor (Biosense Webster, Inc.) will be responsible for the following:

[figure not shown]
- Conduct pre-study site assessment and approval.
- Create and modify (if applicable) study documents including but not limited to the protocol, case report forms (CRFs), and informed consent.
- Select appropriately qualified and trained individuals, including monitors, to conduct the study.
- Conduct protocol and device training for investigators and research personnel as applicable.
- Establish study-specific committees for study oversight.
- Obtain signed study contracts from investigators/hospitals, contract research organizations (CROs), and other involved parties.
- Ship investigational devices to each site.
- Monitor sites for the duration of the study.
- Maintain study database.
- Inform investigator of his/her responsibilities.
- Submit and obtain approval for study from applicable regulatory agencies.

[figure not shown]
- Prepare reports summarizing the status of the study no less than annually. These reports will be supplied to the Principal Investigator at each site.
- Prepare and submit final clinical study report to applicable regulatory agencies.
- Update Report of Priors, instructions for use (IFU), investigator's brochure (IB), and Risk Analyses, as applicable.
- Prepare and update investigators on safety issues, if needed.
- Report to study investigators and regulatory agencies, as required.
- Have AEs reviewed by the study specific committees and/or study specific reviewers, as required.
- Communicate with the Food and Drug Administration (FDA) / Competent Authority (CA) as needed.
- Submit any amendments to the Clinical Study Protocol/Investigational Plan to the FDA/CA.

[figure not shown]
